5.7 DISCHARGE EXAMINATION

The subject is discharged from the hospital after standard post-procedure recovery. The subject will have a physical exam to assess dAVF symptoms; this exam should be completed within 2-days post-procedure. The investigator/designee will collect routine post-procedure routine clinical chemistry and hematology labs before

discharge, record discharge status information, including hospital length of stay, and occurrence of any postoperative adverse events in the eCRF.

5.8 Supplemental PHIL procedure

Complete treatment of the target dAVF may require one or more PHIL procedures. Additional procedure(s) are to be scheduled and performed at the treating physician's discretion. It is estimated that up to seven (7) PHIL procedures may be required to treat the fistula. The physician shall determine the number of treatment procedures based on factors specific to each patient, such as dAVF size, number of feeders, fistulous connections, and location relative to eloquent territory. The treating physician should discontinue PHIL treatment if reflux into an eloquent artery is observed during the procedure.

The supplemental PHIL procedure consists of pre-procedure physical exam to assess dAVF symptoms, collection of routine clinical chemistry and hematology labs pre-procedure, pre-placement imaging, study device placement and post-placement imaging. Subjects require no special preparation for the procedure beyond standard of care for endovascular neuro-interventions. Investigators at their discretion may elect to pre-medicate with antiplatelet agents.

It is expected that the majority of PHIL initial and supplemental embolization procedures are completed under general anesthesia but a minority of procedures may be completed under conscious sedation, depending upon the center's standard of care. Heparin is administered according to standard practices. The PHIL device should be used per the IFU provided in the PHIL packaging. The supplemental PHIL procedure will be performed only by the physician investigator(s) trained by the Sponsor or its designee to perform the procedure.

The investigator will record key characteristics of the device and procedure in the study's eCRF. The investigator will also record technical events/device malfunctions. Radiation exposure will be recorded as absorbed radiation dose and cumulative fluoroscopy time will be recorded. The investigator will retain and provide to the sponsor all images taken during or immediately after the study procedure (including any not specified above).

5.8.1 DISCHARGE EXAMINATION

The subject is discharged from the hospital after standard post-procedure recovery. The subject will have a physical exam to assess dAVF symptoms; this exam should be completed within 2-days post-supplemental procedure. The investigator/designee will collect routine post-procedure clinical chemistry and hematology labs before discharge, record discharge status information, including hospital length of stay, and occurrence of any postoperative adverse events in the eCRF.

5.9 FOLLOW-UP

Subjects will undergo follow-up at a location designated by the research staff at 30 days, 3 months and 6 months following completion of treatment. The investigator will document all findings in the eCRF.

5.9.1 30 DAY (-14 / +14 DAYS)

This visit is to be conducted 30 days following completion of the last PHIL treatment. At this visit, the subject will undergo

- Neurological assessment by Modified Rankin Scale (mRS)
- Neurological assessment by NIH Stroke Scale (if applicable)
- Hemorrhage assessment by Hunt and Hess Stroke Scale (if applicable)
- Assessment dAVF symptoms

- Collection of routine clinical chemistry and hematology labs.
- Record adverse events as reported by participant or observed by investigator.
- Angiographic assessment if the subject presents with symptoms relating to the treated dAVF (DSA, CTA or MRA is acceptable).

5.9.2 3 MONTH VISIT (-2 / + 4 WEEKS)

This visit is to be conducted 3 months following completion of the last PHIL treatment. At this visit, the subject will undergo

- Neurological assessment by Modified Rankin Scale (mRS)
- Neurological assessment by NIH Stroke Scale (if applicable)
- Hemorrhage assessment by Hunt and Hess Stroke Scale (if applicable)
- Assessment dAVF symptoms
- Collection of chemistry and hematology labs
- Record adverse events as reported by participant or observed by investigator.
- Angiographic assessment (if applicable)

5.9.3 6 MONTH VISIT (-3/+6 WEEKS)

This visit is to be conducted 6 months following completion of the last PHIL treatment. At this visit the subject will undergo

- Neurological assessment by Modified Rankin Scale (mRS)
- Neurological assessment by NIH Stroke Scale (if applicable)
- Hemorrhage assessment by Hunt and Hess Stroke Scale (if applicable)
- Physical exam to assess dAVF symptoms
- Collection of chemistry and hematology labs
- Subject self-reported QOL questionnaire using EQ-5D
- Record adverse events as reported by participant or observed by investigator.
- Angiographic assessment

5.10 UNSCHEDULED VISIT

Unscheduled visits are those that take place after the study procedure and before the subject completes the study follow-up period (6 months following completion of the last PHIL treatment). Any visit by the subject to the Investigator related to the target dAVF treated or a potentially associated adverse event should include a neurologic examination using mRS, an assessment of dAVF symptoms, and angiography, as per standard of care. The Investigator should document the review of the adverse event status.

5.11 MISSED VISIT

Any study subject who does not attend a scheduled follow-up visit should be contacted by site personnel to determine the reason for the missed appointment(s). If the missed visit was due to an adverse event (AE), an AE electronic Case Report Form (eCRF) must be completed and any reporting requirements met.

5.12 Special circumstances

On January 31, 2020, the Department of Health and Human Services (HHS) issued a declaration of a public health emergency related to COVID-19 and mobilized the Operating Divisions of HHS. On March 11, 2020, the World Health Organization declared COVID-19, the coronavirus infection, a pandemic. In addition, on March 13, 2020, the

President of the United States declared a national emergency in response to COVID-19. Local officials have issued recommendations limiting non-essential public gatherings. As a result of quarantines, clinical site closures and/or travel limitation, study patients may not be able to return the clinical study sites to complete follow-up visits.

For the remainder of the COVID-19 pandemic, telephone follow-up visits for safety information may be conducted for the 30 day, 3 month, and 6 month visits for any study patient who cannot return to a clinical study site. A list of visits that deviated from the follow-up schedule in clinical protocol Revision B as related to COVID-19 will be provided. The 6 month follow-up visit window is extended to -3 / + 20 weeks to collect additional follow-up information including blood tests and angiography to assess the continued safety and probable benefit of the PHIL device. It is anticipated that clinical site operations will return to normal operations (pre COVID-19) by approximately August 2020.

This protocol revision may be implemented without prior approval from Food and Drug Administration and/or Institutional Review Boards as noted in the guidance document, FDA Guidance on Conduct of Clinical Trials of Medical Products during COVID-19 Pandemic, issued March 2020.

5.13 STUDY SPECIFIC PROCEDURES

The following procedures and/or assessments that will be completed during the study are considered study specific.

- Quality of life with EQ-5D
- Clinical chemistry and hematology at 30 day and 3 month follow-up

5.14 STANDARD OF CARE PROCEDURES

The following procedures and/or assessments that will be completed during the study are considered standard of clinical care.

- Review medical history
- Fistula classification
- CT angiography / MR angiography
- Embolization to occlude blood vessels
- Neurologic assessment with modified Rankin Scale
- Neurologic assessment with NIH Stroke Scale
- Hunt and Hess Stroke Scale score
- Clinical chemistry and hematology before the procedure, after the procedure and at 6 month follow-up.

5.15 STUDY EXIT

Upon completion of the specified study follow-up the subject will be exempt from further data collection. The subject will be seen by the treating physician according to standard care following dAVF treatment.

5.16 DEVIATIONS FROM THIS PROTOCOL

A protocol deviation is defined as an event where the Investigator or study personnel did not conduct the study according to the clinical protocol. The deviation may be either on the part of the participant, the investigator, or the study site staff. Deviations shall be reported to the Sponsor regardless of whether medically justifiable or taken to protect the subject in an emergency.

Except for a change that is intended to eliminate an immediate hazard to a subject, the protocol will be followed as written. Subject specific deviations and non-subject specific deviations, (e.g. unauthorized use of a study device outside the study, unauthorized use of a study device by a physician, etc.) will be reported. Investigators will also adhere to procedures for reporting study deviations to their IRB in accordance with their specific IRB's reporting policies and procedures.

Sites with a high rate of protocol deviations will be closely evaluated and are expected to implement corrective actions to prevent further deviations. If a site demonstrates persistent deviations, as described above, the site may be terminated. The sponsor may terminate investigators and/or investigative sites from the study if the rate of protocol deviations is deemed high or subject safety is in question.

For reporting purposes, protocol deviations may be characterized as major or minor using the definitions below in Table 7.

TABLE 7 PROTOCOL DEVIATION SEVERITY	
Deviation Type	Definition
Major deviation:	Any deviation from subject inclusion and exclusion criteria, unauthorized device use, or performing study specific procedures without obtaining written informed consent. Incomplete/inadequate measured outcome data.
Minor deviation:	Deviation from a protocol requirement such as incomplete/inadequate subject testing procedures, follow-ups performed outside specified time windows, etc. Deviations in administrative procedures for documenting informed consent.

Some information collected in this study is not essential to confirming subject eligibility or to the study measured outcomes and will not be considered a deviation if absent.

5.17 Monitoring compliance

Study monitoring will be a continuous process conducted in accordance with 21 CFR 812.46 and applicable Sponsor procedures.

Clinical site monitoring is conducted to ensure that the rights and well-being of human subjects are protected, that the reported study data are accurate, complete, and verifiable, and that the conduct of the study is in compliance with the currently approved protocol/amendment(s) and with applicable regulatory requirement(s).

- Monitoring for this study will be performed by qualified clinical research personnel, or designees, of MicroVention, Inc.
- Details of clinical site monitoring are documented in a Clinical Monitoring Plan (CMP). The CMP describes in detail who will conduct the monitoring, at what frequency monitoring will be done, at what level of detail monitoring will be performed, and the distribution of monitoring reports.

5.17.1 INDIVIDUAL SITE MONITORING

5.17.1.1 SITE SELECTION

The Sponsor or representative of the Sponsor will assess each potential site to ensure the principal investigator and his/her staff has the facilities and expertise required for the study. Sites will be selected based upon a site assessment, appropriate facilities, and the qualifications of the investigator(s). Individual investigators will be

evaluated by the Sponsor based on experience with the intended procedure(s) and ability to conduct the study according to the study protocol.

To participate, a site must meet the following requirements:

- A physician trained in the use of liquid embolics and has a history of treating dAVFs.
- Commitment from the participating physician to pursue details of any safety outcomes.
- Commitment from the participating physician to enroll only subjects meeting the study criteria.
- A dedicated study coordinator who can enter data and respond to queries.
- Internet access (for electronic data capture) in the hospital or clinic setting.
- Be willing to perform necessary documentation (e.g., eCRF).
- Agree to sign and adhere to the Investigator Agreement.

5.17.1.2 SITE TRAINING

The Sponsor or representative of the Sponsor will train each investigational site to the investigational plan. Investigator/Site Personnel will be trained before performing any study-related procedures. All training must be documented. The PHIL procedure will be performed only by the physician investigator(s) trained by the Sponsor or its designee to perform the procedure.

Training to the investigational plan will include the following topics:

- The study objectives and requirements of this protocol
- Device overview (for non-investigator research personnel)
- Device handling procedures
- Instructions for Use (IFU)
- Responsibilities of the investigator/staff
- Consenting procedures
- Reporting requirements (adverse events and protocol deviations)
- eCRF completion and correction procedures
- Protection of subject confidentiality
- Regulatory files
- Study supplies
- General guidelines for good clinical practices, to be conducted by Sponsor only if the site does not have a current good clinical practices training course.

Existing study site personnel who have been delegated new tasks and new study site personnel will undergo training to the investigational plan, as appropriate.

5.17.1.3 SITE INITIATION

The Sponsor or a representative of the Sponsor will conduct a training session with site staff to review the protocol, eCRFs, the informed consent process, IRB/EC involvement and guidelines, responsibilities and obligations, reporting requirements, and general guidelines for good clinical practices (if applicable).

Prior to enrolling subjects at an investigational site, the following documentation must be provided to the Sponsor:

- IRB approval for the Investigational Plan
- IRB and Sponsor approved Informed Consent Form for the study
- Signed Confidentiality Agreement (CDA)
- Signed Clinical Study Agreement (CSA) and if applicable, Sub-I Agreement(s)

- Training log documentation to verify the appropriate study staff has been trained on the protocol, eCRFs, and study conduct.
- Financial disclosure(s) for the PI and Sub-I(s)
- Investigator(s') curriculum vitae (CV)

5.17.1.4 ONGOING SITE MONITORING

Periodic site monitoring visits will be performed during the study by a designated study monitor assigned by the Sponsor. The purposes of the visits are to confirm compliance to the protocol, review regulatory documents, ensure accurate and complete records are being maintained and to compare source documents to completed eCRFs for completeness and consistency. Specific assessments during a monitoring visit include:

- Continued site acceptability
- Compliance to the protocol
- IRB approval status
- Use of the approved informed consent
- Adequacy of source documents
- Complete and accurate eCRFs
- Reporting of adverse events
- Protocol deviations
- Site records

If it is determined during a monitoring visit that there are significant non-compliance issues at a site, including adherence to the protocol or applicable regulatory requirements, the issues will be discussed with the investigator and study coordinator and the site will be instructed how to gain compliance. If continued non-compliance is detected on a subsequent monitoring visit, it may be necessary to terminate site participation in the study.

5.17.1.5 SITE CLOSE-OUT

Upon completion of the study and the final report, a close-out visit will be conducted. The purpose of the visit will be to:

- Review the records retention requirements for the study
- Arrange for the return of all study related materials to the Sponsor
- Review the final IRB requirements for the study

5.17.1.6 Monitoring reports

After each monitoring visit, the monitor will send to the principal investigator an e-mail or letter summarizing the monitoring visit. A monitoring report will be sent to the Sponsor. The report will include the date of the monitoring visit, the site name, the name of the monitor, the name of the investigator, the names of other individuals present for the monitoring visit, items reviewed during the visit, findings, and any required follow-up. The principal investigator will be responsible for ensuring that follow-up action items requiring resolution at the site are completed in an accurate and timely manner.

5.17.2 OVERALL DATA MONITORING

The Sponsor/designee will monitor all AE reports to identify and trend all events that would require temporary discontinuation of study enrollment, to fully characterize device safety, to modify the study protocol, or to terminate the study.

6 ASSESSMENT OF PROBABLE BENEFIT

The following outcomes will be measured intra-operatively:

- Angiographic occlusion of the pre-specified target vessel(s) intended for treatment at procedure following completion of the first PHIL for treatment procedure
- Angiographic occlusion of the pre-specified target vessel(s) intended for treatment at procedure following completion of all PHIL treatment procedure

The following additional outcomes will be measured:

- Improvement of neurological symptoms
- Number of procedures required to treat the fistula at 6 months follow-up
- Procedure time (defined as first to last fluoroscopic or digital subtraction angiographic acquisitions)
- Radiation exposure (dosage and time)
- Injected volume of PHIL
- Modified Rankin Scale (mRS) at 3 and 6 months follow-up
- Self-reported QOL questionnaire, EQ-5D at 6 month follow-up
- Unplanned adjunctive treatments

Angiographic occlusion of the pre-specified target vessel is defined as cessation of flow at the point of embolic agent administration at the target vessel. It is expected that approximately 60% of the subjects will achieve cessation of flow of the pre-specified target vessel when treated with PHIL.

7 ASSESSMENT OF SAFETY

The aggressive type of intracranial dural arteriovenous fistulae (dAVF) with either direct (non-sinus-type dAVF) or indirect (sinus-type dAVF) retrograde filling of a leptomeningeal vein has a high propensity of ischemia, intracranial hypertension, and cerebral bleeding. ^{11, 14} If left untreated, the mortality rate is 10.4%, the annual bleeding and the non-hemorrhagic neurological deficit risks are 8.1% and 6.9%, respectively. This leads to an annual event-rate of 15%. In the series by Wachter et al of 42 patients who underwent surgical treatment of aggressive dAVFs, the transient and permanent surgical morbidity was 11.9% and 7.1%, respectively. ⁴⁶ Lv et al reported a similar permanent morbidity rate of 7.5% in a series of 40 patients who underwent transarterial dAVF embolization with Onyx. ⁴⁰

The following outcomes will be measured:

- The proportion of subjects with neurological death or any ipsilateral stroke within the first 30 days following completion of the first PHIL treatment procedure.
- The proportion of subjects with neurological death or any ipsilateral stroke within the first 30 days following completion of all PHIL treatment procedures.
- New-onset or worsening of permanent morbidity at 6-month follow-up.
- New-onset Intracranial hemorrhage at 6-month follow-up.
- New-onset of cranial nerve palsy at 6 month follow-up
- Clinically significant technical complications during the procedure including but not limited to reflux of embolic material, migration of the embolic material, catheter entrapment or damage, and vessel dissection.
- Device-related adverse events at procedure and 30 days.
- Device-related mortality at procedure and 30 days.
- Procedure related adverse events including complications of arterial puncture, contrast-induced nephropathy, radiation-induced injuries, renal and anesthesia-related complications.

New-onset of device- or procedure-related neurological deficit or adverse event, or worsening of a previous neurological complaint, disorder, deficit, or adverse event that is unresolved at 6 month follow-up even if not associated with a change in mRS.Intracranial hemorrhage (ICH) is defined as hemorrhage within the fixed vault of the cranium (skull).

Neurologic death is subject death reported as having resulted from a neurologic cause.

Stroke is defined as a new focal neurological deficit in a defined vascular distribution of abrupt onset with symptoms persisting for >24 hours AND a neuro-imaging study or other quantitative study that does not indicate a different etiology. This includes ischemic and hemorrhagic strokes.

It is expected that fewer than approximately 15% of subjects will experience neurologic death or a stroke within the first 30 days following completion of the first PHIL procedure treatment.

7.1 PROCEDURE FOR ADVERSE EVENT REPORTING

Any medical condition that is present at the time that the subject is screened will be considered part of the subject's baseline medical history and not reported as an adverse event. However, if the subject's condition deteriorates at any time during the study, it may be recorded as an AE. Adverse events will be collected from the point of enrollment in the study until a subject exits the study.

Information to be collected includes event description, time of onset, clinician's assessment of severity, relationship to study product (assessed only by those with the training and authority to make a diagnosis), and time of resolution/stabilization of the event. AEs will be categorized using the definitions in Section 7.2. All AEs collected during the study must be followed by the Investigator until resolution or until the end of the 6 month follow-up. All applicable AEs occurring while on study must be documented appropriately regardless of the relationship.

A list of potential anticipated adverse events is provided in Section 1.3.2. AE reporting responsibilities are described in Section 7.2.

Changes in the severity of an AE will be documented to allow an assessment of the duration of the event at each level of severity to be performed.

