3.2 SECONDARY MEASURED OUTCOMES

The following outcomes will be measured:

- The proportion of subjects with neurological death or ipsilateral stroke within the first 30 days following completion of all PHIL treatments
- Angiographic occlusion of the pre-specified target vessel intended for treatment at procedure following completion of all PHIL treatments
- New-onset or worsening of permanent morbidity at 6 month follow-up
- New-onset intracranial hemorrhage at 6 month follow-up
- New-onset of cranial nerve palsy at 6 month follow-up
- Clinically significant technical events during the PHIL embolization procedure(s) including but not limited to reflux of embolic material, migration of the embolic material, catheter entrapment or damage, and vessel dissection.
- Device-related adverse events at procedure and 30 days
- Device-related mortality at procedure and 30 days
- Procedure related adverse events including complications of arterial puncture, contrast-induced nephropathy, radiation-induced injuries, renal and anesthesia-related complications.

New-onset of device- or procedure-related neurological deficit or adverse event, or worsening of a previous neurological complaint, disorder, deficit, or adverse event that is unresolved at 6 month follow-up even if not associated with a change in mRS.Permanent morbidity is defined as a worsening of mRS score at 6 month follow-up compared to the baseline mRS score of:

- ≥1 point in subjects experiencing a stroke
- ≥2 points in subjects experiencing neurological adverse events.

Note, worsening mRS scores associated with non-neurological causes, resulting in limitations to the subject's ability to walk or require assistance to attend to own bodily needs, will not be considered permanent morbidity. This includes medical events such as, bone fractures, muscle, ligament and tendon injuries, and other physical injuries.

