7.2.1 DEFINITIONS

An **Adverse Event** (AE) is defined as any untoward medical occurrence, unintended disease or injury, or untoward clinical signs (including abnormal laboratory findings) in subjects, users or other persons, whether or not related to the investigational medical device. (ISO 14155:2011 3.2)

- NOTE 1: This definition includes events related to the investigational medical device or the comparator.
- NOTE 2: This definition includes events related to the procedures involved.
- NOTE 3: For users or other persons, this definition is restricted to events related to investigational medical devices.

A **Serious Adverse Event** (SAE) is defined as an adverse event that

- a) Led to death,
- b) Led to serious deterioration in the health of the subject, that either resulted in
 - i. A life-threatening illness or injury, or
 - ii. A permanent impairment of a body structure or a body function, or
 - iii. In-subject or prolonged hospitalization, or
 - iv. Medical or surgical intervention to prevent life-threatening illness or injury or permanent impairment to a body structure or a body function,
- c) Led to fetal distress, fetal death or a congenital abnormality or birth defect (ISO 14155:2011 3.37)

NOTE: Planned hospitalization for a pre-existing condition, or a procedure required by this protocol, without serious deterioration in health, is not considered a serious adverse event.

An **Unanticipated Adverse Device Effect** (UADE) is defined as any serious adverse effect on health or safety or any life-threatening problem or death caused by, or associated with, a device, if that effect, problem, or death was not previously identified in nature, severity, or degree of incidence in the investigational plan or application (including a supplementary plan or application), or any other unanticipated serious problem associated with a device that relates to the rights, safety, or welfare of subjects. (21 CFR 812.3 (s))

Severity:

- Mild: No limitation of usual activities, no therapy or only symptomatic therapy required to treat the injury or illness.
- Moderate: Some limitation of usual activities or specific therapy is required.
- Severe: Inability to carry out usual activities, hospitalization, emergency treatment, life threatening events, or death.

Relatedness:

• Study Disease-related: Event is clearly attributable to the underlying study disease state with no temporal relationship to the device, treatment, or medication.

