#### **4.2 Secondary Measured Outcomes**

The following outcomes will be measured:

- The proportion of subjects with neurological death or ipsilateral stroke within the first 30 days following completion of all PHIL treatments
- Angiographic occlusion of the pre-specified target vessel intended for treatment at procedure following completion of all PHIL treatments

- New-onset or worsening of permanent morbidity at 6 month follow-up
- New-onset intracranial hemorrhage at 6 month follow-up
- New-onset of cranial nerve palsy at 6 month follow-up
- Clinically significant technical events during the PHIL embolization procedure(s) including but not limited to reflux of embolic material, migration of the embolic material, catheter entrapment or damage, and vessel dissection.
- Device-related adverse events at procedure and within 30 days
- Device-related mortality at procedure and within 30 days
- Procedure related adverse events including complications of arterial puncture, contrast induced nephropathy, radiation-induced injuries, renal and anesthesia-related complications.
- New-onset of device/procedure-related neurological adverse event or worsening of previous neurological deficit unresolved at 6 month follow-up.

Permanent morbidity is defined as a worsening of mRS score at 6 month follow-up compared to the baseline mRS score of:

- $\geq 1$  point in subjects experiencing a stroke
- $\geq 2$  points in subjects experiencing neurological adverse events.

Note, worsening mRS scores associated with non-neurological causes, resulting in limitations to the subject's ability to walk or require assistance to attend to own bodily needs, will not be considered permanent morbidity. This includes medical events such as, bone fractures, muscle, ligament and tendon injuries, and other physical injuries.

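### Recording the deterioration of a baseline condition as an adverse event is optional, so non-stroke worsening of an existing deficit can be left out of the permanent-morbidity rate although the mRS was measured

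*Protocol*

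**What the plan says.** Protocol Section 7.1 sets the recording rule. A condition present at screening "will be considered part of the subject's baseline medical history and not reported as an adverse event". The next sentence deals with later decline: "if the subject's condition deteriorates at any time during the study, it may be recorded as an AE". The same section also states a general duty: "All applicable AEs occurring while on study must be documented appropriately regardless of the relationship". Section 7.2.1 defines an adverse event broadly, as "any untoward medical occurrence, unintended disease or injury, or untoward clinical signs (including abnormal laboratory findings" and so on, whether or not related to the device.

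Permanent morbidity at 6 months is a secondary safety outcome. Protocol 3.2 and SAP 4.2 define it identically, as worsening of the mRS from baseline by either:

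- at least 1 "point in subjects experiencing a stroke", or
- at least 2 "points in subjects experiencing neurological adverse events".

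A note under the definition removes worsening that has a non-neurological cause, such as a fracture. Stroke is "a new focal neurological deficit in a defined vascular distribution of abrupt onset with symptoms persisting for >24 hours", with imaging or another quantitative study that does not point to a different cause.

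A separate secondary outcome, in Protocol 3.2 and Section 7, covers "worsening of a previous neurological complaint, disorder, deficit, or adverse event that is unresolved at 6 month follow-up", even without a change in mRS. SAP 4.2 and 8.3 give a shorter form in which worsening of an earlier deficit stands as an alternative to a new adverse event.

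**The concern.** Permanent morbidity is the outcome that turns the mRS into a safety rate, and entry to it is through an event: a stroke or a neurological adverse event. For a new problem this is harmless, because a new neurological problem must be documented as an adverse event. For a problem already present at baseline, the one sentence in the protocol that deals with its deterioration leaves recording optional. The choice falls to an unblinded treating site in a single-arm study.

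The eligible population makes the case realistic. Subjects with a baseline mRS up to 3 may enter (Protocol 4.2), and Table 2 lists cranial nerve palsies and loss of motor function among the presenting features. At stake is whether the reported rate contains every neurological decline of the stated size, or only those that a site chose to write up as events. Any error runs in one direction, towards a lower rate.

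**Working it through.** This is a question of definitions, so the main check sets the rules side by side. The arithmetic only gives a scale.

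**Step 1. The plan's only sample-size figure.** Protocol 8.1 and SAP Section 6 enrol 75 to obtain 6-month follow-up in 60, allowing 15 losses. 15/75 = 20%, and 60/(1 − 0.20) = 75, so the figure reproduces. There is no alpha, power or margin to check, and the point does not depend on any.

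**Step 2. Trace one subject through the definition.** Suppose a subject has a baseline deficit and mRS 1. The deficit worsens gradually, the 6-month mRS is 3, and the site enters no adverse event.

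- Stroke branch: not met. The deficit is neither new nor of abrupt onset.
- Neurological adverse-event branch: the change of 3 − 1 = 2 points meets the size criterion, but no adverse event is on file, and Section 7.1 permits that.
- Result: not counted as permanent morbidity, although both mRS values are in the database.

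**Step 3. Look for another route into the rate.**

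- The mRS is taken at baseline, 30 days, 3 months and 6 months (Protocol Table 6 and Section 5.9). SAP 8.4 reports it as counts per category at 3 and 6 months. That table is not conditional on an adverse event, but it does not show within-subject change, so one subject's decline can be offset by another's improvement. The decline would appear in the individual listings (SAP 8.1).
- At follow-up the NIHSS is required when there are signs of a new-onset deficit (Table 6, note 2). Worsening of an old deficit does not trigger it.
- The committee adjudicates primary and secondary outcomes (Protocol 7.4). Nothing says that an mRS decline without an adverse event is sent to it.

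**Step 4. Check the unresolved-worsening outcome in the same way.** The protocol lists complaint, disorder, deficit and adverse event as alternatives, and the SAP separates a new adverse event from worsening of an earlier deficit. The subject in Step 2 fits the worsening branch if the worsening is unresolved at 6 months. No recorded adverse event is required.

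**Step 5. Scale.** With n = 60 evaluated, one omitted subject changes the rate by 1/60 = 1.7 percentage points. The documents give no frequency of unrecorded deterioration, so the range below is an assumption: 5 true cases, 0 to 3 omitted, with the Clopper-Pearson 95% limits that SAP 8.3 specifies.

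| Omitted | Counted | Rate | 95% CI |
|---|---|---|---|
| 0 | 5/60 | 8.3% | 2.8 to 18.4 |
| 1 | 4/60 | 6.7% | 1.8 to 16.2 |
| 2 | 3/60 | 5.0% | 1.0 to 13.9 |
| 3 | 2/60 | 3.3% | 0.4 to 11.5 |

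**The case against.** The best defence reads the documents as a whole. The definition speaks of subjects who experience a neurological adverse event, not of subjects with one on file. The adverse-event definition is wide enough to include worsening. Protocol 1.3.2, to which Section 7.1 refers for anticipated events, lists progressive neurological symptoms related to the fistula. Serious deterioration with permanent impairment is a serious adverse event under 7.2.1, and 7.2.1 has a relatedness category for the study disease. On this reading the permissive sentence merely lifts the medical-history exclusion, and the general duty to document then applies. Monitors also compare source documents with the eCRF, and at least three independent physicians adjudicate the outcomes. Exclusion 1 removes some subjects with confounding deficits at entry.

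Much of this stands, and it makes omission less likely. It does not remove the discretion. The general duty covers adverse events that are *applicable*, and the only sentence specific to deterioration of a baseline condition says *may*. A site can follow the text and enter nothing.

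Three stronger readings are tempting, and the documents do not support them.

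- *That the unresolved-worsening outcome has the same gap.* It does not, as Step 4 shows. Neither document names the data source for its worsening branch, but that it would be built from adverse-event records is inference.
- *That worsening of an existing deficit is a main form of treatment harm.* In Protocol Table 5 only one entry is worded as a worsening (ataxia, 1 subject). The others are mostly new palsies, strokes, haemorrhages and technical events.
- *That omissions would move the rate across the 7.1% and 7.5% literature figures in Protocol Section 7.* With 6 true cases and 2 omitted, 10.0% (3.8 to 20.5) becomes 6.7% (1.8 to 16.2), which crosses both. From 6 with 1 omitted, 8.3% stays above both; from 5 with 1 omitted, 6.7% falls below both; with 4 or fewer true cases the rate is never above either. Crossing thus depends on the assumed count, the intervals overlap heavily, and the plan sets no threshold for this outcome.

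It is also fair to say that deriving morbidity from the mRS alters the definition of a secondary outcome and does more than clarify it.

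**Conclusion.** The point holds for one outcome. Optional recording in Protocol 7.1 does not fit a permanent-morbidity definition that depends on an adverse event, and non-stroke worsening of a baseline deficit by two or more mRS points can drop out of the rate at the site's discretion.

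The size is 1.7 percentage points per omitted subject on 60 evaluated. The number omitted is unknown and may be zero. The conclusion rests on two assumptions: that at least some subjects enter with a deficit that can worsen, and that some sites would take the permissive wording at face value.

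The analysis is descriptive, so type I error, power and decision rules are untouched, and both primary outcomes are outside this point. The severity is moderate: a cheap improvement, not a condition for the study to be interpretable.

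**What to change.** - **Protocol 7.1:** change *may* to *shall* for deterioration of a pre-existing neurological symptom or deficit.
- **Protocol 3.2, SAP 4.2 and SAP 8.3:** derive permanent morbidity from the 6-month mRS change from baseline (at least 2 points, or at least 1 point with stroke) whether or not an adverse event was entered. Exclude only cases that the committee adjudicates as non-neurological under the note already in the definition.
- **Data review:** list every subject whose mRS worsened with no matching adverse event, query the site, and send the case for adjudication.

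The cost is a change of wording in both documents, one listing and a little more data review. The derivation uses mRS values that the schedule already requires. The reported morbidity rate may rise slightly. Because the outcome definition changes, the SAP should state the change and its reason.
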